7.2 PROPOSED ANALYSES

Formal analysis will take place in the last six months of the study after recruitment is complete.

Analysis will require 4 months of expert statistical input. [name], Professor of Bioinformatics at Nottingham Trent University, has great expertise in cancer systems biology, identification of biomarkers, development of prognostic indices and application of statistics to medical diagnostics. At the start of the study he will oversee design of the case report forms to ensure that all relevant data fields are captured and he will carry out data analysis in the final quarter of the study.

Analysis:

1) Comparing incremental sensitivity and specificity between DM and CE-DBT:

True and false positive and negative rates in comparison with histopathology will be computed for each modality, at individual lesion level. BIRADS 1&2 will be considered negative and 3-5, positive. Shifts in BIRADS classifications between modalities will be analysed, to identify differences in diagnostic certainty. Receiver Operator Characteristic curves will be utilised as a standard for evaluation of classification performance.

2) Comparing performance between CE-DBT and MRI for local staging:

Malignant lesions classified as unifocal: measurement accuracy will be compared (whole tumour diameter variance in mm from histological size). Diagnostic accuracy for additional lesions (not detected clinically or seen at initial diagnostic DM) will be compared between CE-DBT and MRI using the methods described in #1.

3) The analyses described above will be applied to explore variations in differential performance between CE-DBT and MRI:

- a) by breast density
- b) by age
- c) by levels of BPE
- d) by tumour subtype (invasive lobular versus invasive ductal carcinomas)

We will explore enhancement intensity and temporal patterns of enhancement according to histopathological tumour type and grade.

7.3 MISSING DATA

Every effort will be made to chase up missing data, failing this any patient with essential data missing will be excluded from the analysis.

Patients will be withdrawn if they do not complete the full CE-DBT protocol or if they fail to proceed directly to surgical treatment. Failure to tolerate the MRI will not necessarily result in the patient being withdrawn, as it will still be possible to compare CE-DBT findings with the gold standard surgical pathology.

7.4 TRANSFER OF DATAStatistical analysis will necessitate secure transfer of anonymised data taken from the secure server housing the electronic case report forms to the study statistician.

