1 INTRODUCTION

It is well established that digital mammography (DM) has limitations in the diagnosis of breast cancer in both symptomatic and screening populations¹. This is largely attributable to obscuration of masses by overlapping normal fibroglandular parenchyma, particularly in women with dense breasts, seen in up to 40% of Scottish women. Even with state-of-the-art DM, sensitivity in the dense breast can be under 60%². In the symptomatic clinic setting, diagnostic uncertainty about the presence and extent of breast cancer can persist, even after complementary breast ultrasound. This can necessitate subsequent supplemental tests such as breast magnetic resonance imaging (MRI) to allow treatment planning.

The shortfalls of DM have been partly addressed by development of two novel mammographic techniques.

Digital breast tomosynthesis (DBT) is a quasi-3D mammographic technique, which improves visibility of malignant structural features, particularly spiculation. Its ability to resolve composite opacities also increases specificity compared with DM. Published studies show increased cancer detection rates of 20-30%, with a concurrent reduction in recall rates in the screening setting³. Research by our group and others has established that DBT can accurately characterise indeterminate mammographic abnormalities detected at screening⁴.

Contrast-enhanced spectral mammography (CESM) is a 2D mammographic technique yielding functional information on the vascularity of breast lesions through dual energy subtraction. It enables the neovascularisation of malignant tumours to be detected. The diagnostic accuracy of CESM in the literature is better than DM and comparable to MRI, with sensitivities over 90%⁵⁻⁷. This is despite the fact that timings of image acquisition after contrast medium administration are quite different between CESM and MRI.

Spiculation, the feature highlighted by DBT, is most frequently seen in low grade, relatively indolent breast cancers⁸. Conversely, the pathological process underpinning visualisation of tumours at CESM, neoangiogenesis, is more pronounced in aggressive high grade cancers, which may appear paradoxically benign at DM and DBT⁹.

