3 STUDY OBJECTIVES & OUTCOMES

The aim of this study is to evaluate the performance of CE-DBT in the identification and local staging of symptomatic breast cancer. The primary objective is to determine the incremental increase in sensitivity of CE-DBT over DM alone in women with symptoms/signs suspicious for breast cancer, the latter currently being standard of care. This will be assessed through comparison with post-surgical pathology in all women with biopsy-proven breast cancer treated with primary surgery.

The second objective is to assess the accuracy of local cancer staging with CE-DBT regarding extent and the presence/ absence of multifocality. All patients with biopsy-proven breast cancer will undergo breast MRI, since this is the current imaging gold standard and a head to head comparison of CE-DBT and MRI against surgical pathology will be made.

Thirdly, planned subset analysis will explore the influence of age, breast density, and BPE on the diagnostic performance of CE-DBT. In order to address this, participants will undergo CESM of the index breast at two time points to enable semi-quantitative kinetic analysis of lesional and background contrast enhancement in comparison to breast MRI to determine whether this affects diagnostic performance.

Finally the study will explore the accuracy of CE-DBT in the subset of women who would normally receive pre-operative breast MRI as standard of care and will aim to identify clinicopathological features influencing the accuracy of CE-DBT in a planned subset analysis.

Table 1: Primary Objectives and Outcome Measures

Primary Objective:	Outcome Measure:	Timepoint of outcome measured
Diagnostic performance of CE- DBT in the diagnosis of breast cancer	Incremental sensitivity of CE-DBT versus DM, compared to gold- standard surgical pathology	Final 6 months of study

Table 2: Secondary Objectives and Outcome Measures

Secondary Objective:	Outcome Measure:	Timepoint of outcome measured
Assessment of comparative accuracy of CE-DBT and MRI in local staging of breast cancer	Variance between CE-DBT, MRI and pathology	Final 6 months of study
Comparison of specificity of CE- DBT versus breast MRI at breast level	Number of false positive examinations (score 3 or above) with each imaging modality	Final 6 months of study

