4.10 NUMBER OF PARTICIPANTS

The study aims to recruit 200 women with clinical suspicion of breast cancer. Analysis of data from the symptomatic clinics at Ninewells Breast Unit (NHS Tayside) shows that around 75% of these (150) will subsequently prove to have breast cancer on biopsy. With a conservative estimated consent rate of 50% and screen failure rate of between 10-20% this equates to a recruitment rate of one to two patients per week over 2 years, the anticipated recruitment period.

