5.5 WITHDRAWAL PROCEDURES

- Participants will be withdrawn if the CE-DBT examination is not completed.
- Any women declining needle biopsy will be withdrawn from the study because it will not be possible to determine a definitive diagnosis.
- Participants:
 - Who, after a diagnosis of breast cancer, prove unsuitable for initial surgical treatment (severe co-morbidities), or
 - \circ Who decline surgery, or
 - Where initial surgical treatment does not occur (e.g. neoadjuvant chemotherapy to allow breast conservation)

Will be excluded from further analysis because full pathological-radiological correlation will not be possible.

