7 STATISTICS AND DATA ANALYSIS

7.1 SAMPLE SIZE CALCULATION

The proposed study is necessarily exploratory given the novelty of the CE-DBT technique. An achievable sample size has been set based on data from the symptomatic breast clinic at Ninewells Hospital (NHS Tayside), where approximately 75% of women with clinically suspicious symptoms and signs prove to have breast cancer. Thus, a consented cohort of 200 women including 150 with cancer is realistic and achievable. Our recent study (as yet unpublished) of DBT in the symptomatic setting has shown a 15% gain in sensitivity over DM in dense breasts. From the literature, CESM has a sensitivity over 90%¹¹⁻¹³.

Thus, assuming a sensitivity for DM of 70%, the CI and study statistician calculate that a sample size of 120 is adequately powered to show an increase in sensitivity of CE-DBT of 10%.

Allowing for a 10-20% examination contraindication rate, it is considered that there will be enough participants - 150 with cancer - covering a sufficient range of characteristics (e.g. lobular cancer [12% of symptomatic invasive cancers in women under 70 in our practice], mammographically occult cancer) to enable us to advance knowledge concerning the most promising applications of CE-DBT, and to generate sufficient preliminary data for robust power calculations using appropriate models (TT test and Chi squared power models) for subsequent full-scale clinical effectiveness and cost-effectiveness studies.

It is challenging to maximise recruitment to studies within a busy clinical service, but we have considerable experience of overcoming such challenges. Multidisciplinary communication and co-ordination are key to success and we are fortunate in having a population of patients who are very interested in participating in research, even without perceived benefit to themselves. At least 4 clinically suspicious cancers are seen per week, representing 75% of all clinically suspicious presentations. Thus 200 participants (150 with cancer) could be recruited over two years assuming a 50% consent rate.

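### The surgery requirement removes biopsy-proven cancers from the CE-DBT versus DM sensitivity analysis after the images are read, with no allowance for the loss, and section 7.3 as worded also withdraws biopsy-benign women needed for specificity

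*Protocol*

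**What the plan says.** Section 3 defines the primary comparison: "This will be assessed through comparison with post-surgical pathology in all women with biopsy-proven breast cancer treated with primary surgery". Section 5.5 excludes from further analysis women who, after a cancer diagnosis, prove unsuitable for initial surgery, women who decline surgery, and cases described as "Where initial surgical treatment does not occur (e.g. neoadjuvant chemotherapy to allow breast conservation". The reason given is that full correlation of pathology with imaging is not possible. Section 7.3 repeats the rule under missing data: patients are withdrawn if CE-DBT is incomplete "or if they fail to proceed directly to surgical treatment". That sentence does not restrict the rule to women with cancer.

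Section 7.2 lists as its first analysis "Comparing incremental sensitivity and specificity between DM and CE-DBT", by lesion and against histopathology, with BI-RADS 3-5 as positive and with ROC curves. On numbers, section 4.10 states "The study aims to recruit 200 women with clinical suspicion of breast cancer" and expects about 75% to have cancer on biopsy. Section 7.1 says "Thus, a consented cohort of 200 women including 150 with cancer is realistic and achievable", calls 120 adequate for a 10-point gain over a DM sensitivity of 70%, and mentions a 10-20% allowance for examination contraindications.

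**The concern.** For the index lesion, the primary question is whether DM and CE-DBT each called a proven cancer positive. The protocol itself treats needle biopsy as the diagnosis: section 4.10 counts cancers on biopsy, and section 5.5 withdraws women who decline biopsy because no definitive diagnosis can then be made. Requiring surgery as well removes cancers whose presence is already established.

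The removal comes after the index test. Under section 4.2, CE-DBT is read in clinic and guides ultrasound and biopsy; under section 4.4, MRI results are reviewed before surgery. A CE-DBT finding could therefore contribute to a change of treatment that takes the woman out of the analysis of CE-DBT. Section 1 gives a reason why excluded cancers might differ: the neoangiogenesis that makes tumours visible on CESM "is more pronounced in aggressive high grade cancers, which may appear paradoxically benign at DM and DBT".

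The second issue is specificity. Section 2 asks whether CE-DBT improves diagnostic accuracy. Under section 4.5 the same reader adds DBT and CESM after DM, so extra positive calls will tend to raise sensitivity. Specificity is the counterweight. If the withdrawal rule were applied as section 7.3 is worded, most of the women with benign biopsies would be lost to it.

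**Working it through.** **Inputs from the protocol.** 200 women; 75% with cancer; DM sensitivity 70%; gain 10 points; 120 cancers required (sections 4.10 and 7.1). Alpha, power, discordance between paired reads and the share of cancers without primary surgery are not stated. They are assumed below and varied where it matters.

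**1. The plan's own figures.** 200 × 0.75 = 150 with cancer; 200 − 150 = 50 without. Both reproduce. The 120 can be reached but not uniquely. The paired (McNemar) sample size is

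n = (1.96·√s + 0.842·√(s − d²))² / d²,

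with d = 0.10, s the total discordance, two-sided 5% and 80% power. It gives 116 at s = 0.15, 124 at s = 0.16 and 155 at s = 0.20. A one-sample, one-sided test of 80% against a fixed 70% gives 119.

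**2. Cancers left under the surgery rule.** With a share e of the 150 not going straight to surgery, 150 × (1 − e) remain: 142.5 at 5%, 135 at 10%, 120 at 20%, 105 at 30%. The margin is used up at e = 1 − 120/150 = 20%. If the 10-20% contraindication allowance also comes off the 150, 135 to 120 remain, and the further loss that can be absorbed is 1 − 120/135 = 11% down to 0%.

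**3. Power.** Power = Φ((d·√n − 1.96·√s) / √(s − d²)), d = 0.10:

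| Discordance s | n = 150 | n = 135 | n = 120 | n = 105 |
|---|---|---|---|---|
| 0.15 | 0.89 | 0.86 | 0.82 | 0.76 |
| 0.16 | 0.87 | 0.84 | 0.79 | 0.73 |
| 0.20 | 0.79 | 0.74 | 0.69 | 0.63 |

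**4. Possible bias.** The gain in all biopsy-proven cancers is (1 − e)·(gain in retained) + e·(gain in excluded). Take e = 20% and a 10-point gain in the retained women, both assumed. If the excluded women gain 0, the overall gain is 0.8 × 10 + 0.2 × 0 = 8 points and the trial overstates it by 2. If they gain 20, it is 0.8 × 10 + 0.2 × 20 = 12 and the trial understates it by 2.

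**5. Specificity.** With about 50 biopsy-benign women and an assumed specificity of 80%, the 95% half-width is 1.96·√(0.8 × 0.2/50) = 11 points. For the paired CE-DBT versus DM difference (taken near zero), 1.96·√(s/50) gives 9, 12 and 15 points at s = 0.10, 0.20 and 0.30. Under the literal wording of 7.3, and if none of these women has surgery, the woman-level denominator is 0.

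**The case against.** The surgery restriction is deliberate and disclosed, and it has a reason. Section 7.2 works at lesion level. A needle biopsy proves cancer only where it sampled, whereas the excised specimen can show foci that both tests missed. A reader might infer that surgical pathology is needed only for size and focality. The documents do not support that, so the surgical set should stay. A biopsy reference also has its own weakness: CE-DBT findings partly decide what is biopsied (section 4.2), and section 4.1 provides no follow-up of benign results.

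A reader might infer that the plan intends to discard the 50 benign women. Section 5.5 points the other way: its list opens with a cancer diagnosis, and the wording of 7.3 presupposes that surgery was due. A reader might also infer that these women alone can supply specificity. They cannot be the only source: both breasts are imaged in every participant, analysis is by lesion, and the specificity outcome in Table 2 compares CE-DBT with MRI by breast. Benign lesions and contralateral breasts in women with cancer can contribute, although an unbiopsied breast has no histology.

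On bias and loss, comorbidity and declining surgery are not decisions about tumour type, and the link to grade is an inference. Many likely neoadjuvant or inoperable cases are screened out at entry (section 4.12), so the loss may be below 20%. The study also calls itself exploratory.

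These objections limit the point. They leave standing the exclusion after reading, the missing allowance and the conflict between 7.3 and 7.2.

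**Conclusion.** The point holds in two parts. First, sections 3, 5.5 and 7.3 remove biopsy-proven cancers from the sensitivity comparison after the index test is read, and section 7.1 makes no provision for it. An assumed 20% loss takes the study exactly to its required 120; 30% takes it to 105. Against the full 150, power at those losses is lower by about 7 to 16 percentage points across discordance of 15-20%. The bias could go either way. A reader might infer that the CE-DBT gain must be understated, or that the trial is necessarily underpowered; neither follows, because the share excluded, their gain and the discordance are all unknown.

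Second, the wording of 7.3 conflicts with the specificity and ROC analysis in 7.2 and must be reconciled with 5.5. About 50 women are affected. This figure rests on the 75% rate from clinically suspicious women; recruits entered on ultrasound findings may differ, and some benign women may have an operation. It is most likely a drafting defect, but a withdrawal rule should not depend on the reader's interpretation.

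**What to change.** 1. Reword 7.3 in line with 5.5 so that the surgery requirement for analysis applies only to women with biopsy-proven cancer. State that biopsy-benign women remain in the CE-DBT versus DM specificity and ROC analysis, with needle biopsy as reference.
2. Keep the surgical-pathology set for lesion-level, size and focality analyses. Add a prespecified index-lesion sensitivity comparison in all biopsy-proven cancers with a completed CE-DBT read, reported beside the surgery-only result.
3. Report the number of women excluded after reading, and the reasons.

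The cost is wording and analysis; section 6.1 already collects the reads and biopsy results. The downside is that, in the added analyses, the reference is partly driven by CE-DBT and benign biopsies have no later confirmation. The report should state this limitation and compare the two sets. Replacing the primary set outright is not recommended, for the same reason.

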8 STUDY MANAGEMENT AND OVERSIGHT ARRANGEMENTS

8.1 STUDY MANAGEMENT GROUP

The study will be co-ordinated by a Study Management Group (SMG), consisting of the CI, study manager, senior trial manager and co-investigators, with the study statistician if necessary and meeting on a monthly basis. The remit of the SMG will include review of day-to-day management of the study, recruitment rates and any problems encountered, according to TCTU protocol.

8.2 STUDY STEERING COMMITTEE

A Study Steering Committee is not required for this non-randomised study and the SMG will subsume this role. However, the CI may point seek advice from an external adviser with the relevant clinical expertise.

8.3 DATA MONITORING COMMITTEE

As this is a small study, data monitoring will be the responsibility of the Study Management Group.

8.4 INSPECTION OF RECORDS

The CI, PIs and all institutions involved in the study will permit study related monitoring, audits, and REC review. The CI agrees to allow the Sponsor or, representatives of the Sponsor, direct access to all study records and source documentation.

9 GOOD CLINICAL PRACTICE

9.1 ETHICAL CONDUCT OF THE STUDY

The study will be conducted in accordance with the principles of good clinical practice (GCP).

In addition to Sponsorship approval, a favorable ethical opinion will be obtained from the appropriate REC and appropriate NHST R&D approval will be obtained prior to commencement of the study.

9.2 CONFIDENTIALITY

All laboratory specimens, evaluation forms, reports, and other records will be identified in a manner designed to maintain participant confidentiality. All records will be kept in a secure storage area with limited access to study staff only. Clinical information will not be released without the written permission of the participant, except as necessary for monitoring and auditing by the Sponsor or its designee. The CI and study staff involved with this study will not

disclose or use for any purpose other than performance of the study, any data, record, or other unpublished, confidential information disclosed to those individuals for the purpose of the study. Prior written agreement from the Sponsor or its designee will be obtained for the disclosure of any said confidential information to other parties.

9.3 DATA PROTECTION

The CI and study staff involved with this study will comply with the requirements of the Data Protection Act 1998 with regard to the collection, storage, processing and disclosure of personal information and will uphold the Act's core principles. The CI and study staff will also adhere, if appropriate, to the current version of the NHS Scotland Code of Practice on Protecting Patient Confidentiality. Access to collated participant data will be restricted to the CI and appropriate study staff.

Computers used to collate the data will have limited access measures via user names and passwords.

Published results will not contain any personal data that could allow identification of individual participants.

9.4 INSURANCE AND INDEMNITY

The University of Dundee and Tayside Health Board are Co-Sponsoring the study.

Insurance – The University of Dundee will obtain and hold a policy of Public Liability Insurance for legal liabilities arising from the study.

Tayside Health Board will maintain its membership of the Clinical Negligence and Other Risks Insurance Scheme ("CNORIS") which covers the legal liability of Tayside in relation to the study.

Where the study involves University of Dundee staff undertaking clinical research on NHS patients, such staff will hold honorary contracts with Tayside Health Board which means they will have cover under Tayside's membership of the CNORIS scheme.

Indemnity The Co-Sponsors do not provide study participants with indemnity in relation to participation in the Study but have insurance for legal liability as described above.

10 ADVERSE EVENTS

10.1 DEFINITIONS

Adverse Event (AE)	Any untoward medical occurrence in a clinical research participant which does not necessarily have a causal relationship with study participation
Serious Adverse Event (SAE)	 A serious adverse event is any untoward medical occurrence that: results in death is life threatening requires hospitalisation or prolongation of existing hospitalisation results in persistent or significant disability or incapacity is a congenital anomaly or birth defect Or is otherwise considered serious

10.2 RECORDING AND REPORTING AE

All SAEs will be recorded on the AE Log in the CRF and will be assessed for severity by the CI or delegate. The occurrence of minor contrast reactions will also be recorded.

SAEs will be recorded from the time a participant consents to join the study until the participant's last study visit, which will generally be for the study-specific MRI examination.

The Investigator will make a clinical judgment as to whether or not an AE is of sufficient severity to require the participant's removal from the study. A participant may also voluntarily withdraw from the study due to what he or she perceives as an intolerable AE; for example, if the patient is unable to tolerate the MRI examination. If either of these occurs, the participant should, if required, be offered an end of study assessment and be given appropriate care under medical supervision until symptoms cease, or the condition becomes stable. SAEs will be followed up until 30 days after participant's last visit. Any adverse events will largely be those related to the administration of intravenous contrast material and are expected to occur within 24-48 hours of administration of intravenous contrast. Clinical progression of the cancer, or hospitalisation for elective treatment (planned before joining the study) will not be classed as SAEs.

The CI or delegate will ask about the occurrence of AEs/SAEs at every visit during the study, which will include the initial clinic visit and the visit for the MRI scan. **SAEs which are both unexpected and related to study participation** will be submitted on an HRA NCTIMP Safety Report form to the REC by the CI, within 15 days of becoming aware of the SAE, and copied to the Sponsor Research Governance Office.

